3.6 Unscheduled visit

The patient may be required to return to the clinic in the morning following a 10-hour fast for an unscheduled Visit for a repeat measurement of fasting blood glucose and any necessary clinical safety laboratory assessments if the investigator deems it necessary. AEs/SAEs assessment will also be performed.

3.7 Self-Monitoring Fasting Blood Glucose and Patient Diaries

All patients will self-monitor fasting morning blood glucose levels three (3) times weekly during the run-in and treatment period. Monitoring must be performed at the same time each designated day (\pm 10 minutes) prior any caloric intake. Patients will be required to record the values in a patient diary and bring the diary to each clinic visit; Information recorded for the fasting blood glucose will be reviewed by the clinical research coordinator for completeness and transcribed onto CRF's. During the study, both fasting finger stick glucose and laboratory fasting plasma glucose will be obtained. Adverse events including hypoglycemia will be monitored from the self-monitoring blood glucose diary and recorded in the CRF.

If a fasting blood glucose measures greater than or equal to 270 mg/dL (15 mmol/L) during daily self-monitoring or during any in-clinic visit, the patient will be required to contact the clinic to report the value. The patient may be required to return for an unscheduled visit to the clinic for a repeat measurement of fasting blood glucose within one week after the original measurement. If the patient is invited for an unscheduled visit, blood will be drawn and sent to lab for plasma glucose determination. If the repeat measurement is also greater than or equal to 270 mg/dL, the patient will be discontinued from treatment with study drug and offered rescue medication. The patient will continue to be seen for all remaining study visits, if possible.

If a fasting blood glucose value is <70 mg/dL, the patient should drink 1 cup of orange juice or swallow 3-4 glucose tablets. The patient must check his blood sugar after 10 min and if the blood glucose level does not raise, the patients needs to drink another cup of orange juice or swallow 3-4 glucose tablets. Blood sugar must be checked again after 10 minutes. The patient must call to report this event to the study site and record all blood glucose levels in the diary.

If three or more fingerstick glucose values of <50 mg/dL (2.78 mmol/L) are observed within 12 hours subsequent to administration of study drug without a reasonable explanation (such as increased physical activity and/or skipped meal), the patient will be discontinued from treatment with study drug and rescued with glucose administration (20g of glucose tablets) which will be available at all times at the study site. This information will be recorded in the patient's diary and

the patient will be instructed to contact the study site if this occurs. The patient will continue to be seen for all remaining study visits.

Sites will instruct patients to immediately perform a finger stick glucose measurement if any symptoms occur that may be related to hypoglycemia (e.g., weakness, dizziness, shakiness, increased sweating, palpitations, or confusion), and to avoid delay in treating these symptoms. The measurements will be recorded in the patient diary. Patients will always carry glucose tablets with them and ingest 3-4 tablets if hypoglycemia occurs.

Hypoglycemia and associated symptoms (e.g., weakness, dizziness, shakiness, increased sweating, palpitations, or confusion), have been associated with insulin administration, including ORMD-0801.

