5.2 IMP Administration

5.2.1 Visit 3 to Visit 8

The treatment regimen (Active) will consist of a soft gelatin capsule containing 8 mg insulin, and 75 mg SBTI. Patients will take 2 capsules daily in the morning 30 to 45 minutes prior to breakfast and no later than 10AM. At Visit 2 (placebo) and at Visits 3, 6, 7, 8 (Active) capsules will be administered in the clinic. Blood samples and weights will be taken prior to dosing, after which the patients will take the drug, so he\she will be provided with a small snack to eat after 30 to 45 minutes.

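### Does fasting-only glucose monitoring, with no fixed order of fingerstick and capsule at home, undermine the 12-hour hypoglycaemia rule?

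*Combined protocol and SAP*

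**What the plan says.** Section 3.7 sets the home schedule: "All patients will self-monitor fasting morning blood glucose levels three (3) times weekly during the run-in and treatment period". Readings are taken at a fixed clock time, within 10 minutes, before any calories.

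For a value below 70 mg/dL the patient takes oral glucose. Then: "The patient must check his blood sugar after 10 min and if the blood glucose level does not raise", oral glucose is repeated, and "Blood sugar must be checked again after 10 minutes". The patient must telephone the site and write all values in the diary.

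The discontinuation rule begins: "If three or more fingerstick glucose values of <50 mg/dL (2.78 mmol/L) are observed within 12 hours subsequent to administration of study drug". It applies only when there is no reasonable explanation, and the patient is told to contact the site if it occurs. Patients are also to "immediately perform a finger stick glucose measurement if any symptoms occur that may be related to hypoglycemia".

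On dosing, Section 5.2.1 says: "Patients will take 2 capsules daily in the morning 30 to 45 minutes prior to breakfast and no later than 10AM". For clinic days it says: "Blood samples and weights will be taken prior to dosing". Section 5.4 assesses compliance by capsule count. Section 5.5 requires administration to be recorded accurately in source documents and CRF, without naming a clock time.

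On adverse events, Section 7.5 lists date and time of onset for every event and makes hypoglycaemic events adverse events. Section 7.5.1 asks for the time on clinic days, if available. Section 8.2.1 lists onset time where available.

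**The concern.** Safety is the primary endpoint (Section 6.3), and hypoglycaemia is the only adverse event of special interest (Section 7.3). An oral insulin might be expected to lower glucose after the dose, yet no post-dose reading is scheduled. A low without symptoms later in the day would be found only by chance.

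The stopping rule is tied to the dose, but the two facts needed to apply it at home, the order of fingerstick and capsule and the dose time, are not written down. The same three values might then stop treatment in one patient and not in another. If sites follow Section 7.5.1 alone, a home event could reach the CRF without an onset time. That would weaken the causality grades in Section 7.6, which depend on temporal sequence, and the tabulation by relationship in Section 8.2.1. It could also bear on the trial pause in Section 4.3, which depends on a reasonable possibility of causation.

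**Working it through.** The plan gives no figure to reproduce: Section 8.1 says the study is not powered, and no hypoglycaemia rate is assumed. The check is a count of readings against the rule, followed by a comparison of sections.

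**Scheduled readings.** Treatment lasts 12 weeks with 3 readings a week: 12 × 3 = 36 per patient, at most one a day.

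- Fingerstick before the capsule: the previous dose was taken by 10:00 the day before. From 10:00 to midnight is 14 h, so the gap is at least 14 h, more than 12 h. In the window: 0 of 36.
- Fingerstick after the capsule: breakfast follows the capsule by 30 to 45 minutes and the reading precedes breakfast, so it comes at most 45 minutes after the dose. In the window: 36 of 36.
- Laboratory values at Visits 6, 7 and 8 are pre-dose: 0 of 3.

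The range from 0 to 36 is the whole possible range, so it shows only that the order is open. It does not decide whether the rule works. The rule needs three values in 12 hours; one scheduled reading a day cannot supply them under either order. It rests on symptom-prompted tests and rechecks.

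**Can one fasting episode meet the count?** A first value and two rechecks give 1 + 2 = 3 values over 10 + 10 = 20 minutes. However, rechecks start below 70 mg/dL while the rule counts values below 50 mg/dL. All three values must be below 50, two of them after oral glucose. On a natural reading the second recheck happens only if the first shows no rise. The dose must have come first, and there must be no reasonable explanation. As for whether rechecks count, the rule is worded in fingerstick values, not episodes.

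**How much does the exact dose time matter?** A dose by 10:00 gives a window that closes by 10:00 + 12 h = 22:00. A low in the middle of the day is inside it whatever the exact minute of dosing. Doubt remains only close to the morning dose or late in the evening.

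**Onset time.** Day 0 to day 84 is 85 days, with six scheduled clinic days (Visits 3 to 8). If Section 7.5.1 stood alone, time would be requested on 6/85 = 7.1% of days and not on 79/85 = 92.9%. It does not stand alone: Section 7.5 asks for time on every event. A site that records the time satisfies both sections.

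**Reading a zero count.** With 0 of 40 patients affected and full detection, the one-sided 95% upper bound is 1 − 0.05^(1/40) = 7.2%. If only half of affected patients were detected (an assumption; the documents give no figure), it is about 7.2%/0.5 = 14.4%. This is a caution for interpretation; no tabulated result changes.

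**The case for a change.** The strongest case for a change is that the rule is meant to operate at home, so its inputs should not depend on what a coordinator thinks to ask. Capsule counts do not give times, the recording requirement in Section 5.5 names no clock time, and two sections disagree on onset time. A sentence or two and a listing column would cost little. A reader of the safety table is not told that silent post-dose lows were not looked for.

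The facts in this stand. The consequences do not. Every value below 70 mg/dL requires a call to the site, so timing can be established while it is fresh and need not be reconstructed from a CRF. Section 4.3 lets the investigator stop a patient for risk whether or not the 12-hour count is met. The trial pause needs a related death or two related Grade 4 events; a serious event carries a signed report within 24 hours with a relatedness assessment (Section 7.5.2), so causality would not hang on a blank time field. Leaving the Per Protocol population would follow from stopping early for any reason, and the supplied text assigns no analysis to that population. The diary and CRF are not in the supplied file, so missing fields cannot be inferred.

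One wording slip is real. Section 3.7 refers to readings "during daily self-monitoring or during any in-clinic visit" after setting three a week. Those two phrases must be reconciled, as must Sections 7.5 and 7.5.1, but both are clerical points on which no result depends.

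**Conclusion.** No change to the plan follows. Fasting-only monitoring is a trade-off the design accepts: post-dose lows come to light through symptoms, rechecks or incidental tests, and the incidence should be read that way. The study is exploratory and descriptive and claims nothing about silent post-dose lows, so the study report is a sufficient place for that caveat.

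The missing order and dose time are details that sites would sensibly settle at the required call. They matter only for readings near the morning dose or late in the evening, and for an episode whose values all stay below 50 mg/dL after oral glucose. How many patients that might be is unknown, because no expected rate is given; if 40 are treated, each is 1/40 = 2.5 percentage points of the safety result. The conclusion assumes that patients make the calls Section 3.7 requires, that sites record onset time as Section 7.5 asks, and that the morning dosing limit is kept.

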4.3 Subject and Trial Discontinuation

Subjects may choose to withdraw from this study at any time for any reason without penalty of jeopardizing their health care or loss of benefits to which the subject is otherwise entitled.

Within the provisions of informed consent and good clinical judgment with respect to safety, every attempt will be made to have subjects complete the study. The following are reasons to terminate a subject's participation in the study:

1. Subject experiences an AE that in the judgement of the Investigator poses a significant risk to the subject for continued participation in the study.
2. Subject uses any medication that in the judgment of the Investigator poses a significant risk to the subject for continued participation in the study or that will interfere with the interpretation of the results of the study.
3. Subject becomes pregnant.
4. Significant protocol violation or noncompliance on the part of the subject or the Investigator.
5. Intercurrent illness that requires treatment that is not consistent with the protocol requirements, or intercurrent illness or the associated treatment that in the judgment of the Investigator poses a significant risk to the subject for continued participation in the study.
6. Subject wishes to withdraw for any reason.
7. Sponsor elects to end the study, or the Investigational Site elects to end the study at their site.
8. Any other reason that in the judgment of the Investigator poses unacceptable risk to the subject.

Subjects who withdraw from the study prior to treatment may be replaced. Subjects who are withdrawn and have received at least one treatment will not be replaced. Subjects who discontinue study drug treatment will not be replaced.

Except in cases of emergency, the Investigator should consult with the Sponsor and the Medical Monitor before removing the subject from the study. In some circumstances it may be necessary to temporarily interrupt treatment as a result of AEs that may have an unclear relationship to the IMP. The Investigator should obtain approval from the Sponsor and Medical Monitor before restarting IMPs that were temporarily discontinued for an AE.

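### Section 3.7 treats a home fasting reading below 70 mg/dL but does not say whether to take that morning's capsules, so a patient who tests first can follow the plan and take insulin just after, or during, a low

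*Combined protocol and SAP*

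**What the plan says.** Section 3.7 requires a fasting finger-stick three mornings a week during run-in and treatment, before any caloric intake. For low values it says: "If a fasting blood glucose value is <70 mg/dL, the patient should drink 1 cup of orange juice or swallow 3-4 glucose tablets". It continues: "The patient must check his blood sugar after 10 min and if the blood glucose level does not raise", the patient takes a second helping and tests once more 10 minutes later. Then: "The patient must call to report this event to the study site and record all blood glucose levels in the diary". That branch says nothing about study drug.

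Two other branches of the section do. For high values: "If the repeat measurement is also greater than or equal to 270 mg/dL, the patient will be discontinued from treatment with study drug". For very low values, the drug is stopped when three or more readings below 50 mg/dL "are observed within 12 hours subsequent to administration of study drug without a reasonable explanation".

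Sections 3.4.2 and 5.2.1 set the dose at two capsules each morning, 30 to 45 minutes before breakfast and by 10 AM. Section 5.3 plans no dose modification and keeps dosing daily unless the discontinuation criteria of Section 4.3 are met. Section 4.3 contains no glucose threshold. It does allow participation to end when "Subject experiences an AE that in the judgement of the Investigator poses a significant risk", and it adds: "In some circumstances it may be necessary to temporarily interrupt treatment as a result of AEs".

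Neither Section 3.7 nor Table 1 states whether the finger-stick comes before or after the capsules.

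**The concern.** A fasting low found before the dose is the one moment when the patient knows that glucose is low and has not yet taken the day's insulin. The plan tells the patient how to treat it, but the only text that bears on the capsules is the daily-dosing rule.

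The recheck makes this sharper. It asks whether glucose has risen, not whether it has reached a safe value. A rise from 52 to 58 mg/dL, for example, would satisfy it. If the second recheck is still low, the only remaining step is the call. That call has no stated timing relative to the dose, and the protocol does not say what the site should advise. With 7 or 8 planned sites in three countries (Section 8.1), the answer may be dose, delay or skip.

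Safety is the primary endpoint (Section 6.3), and hypoglycaemia is the only adverse event of special interest listed (Section 7.3). Section 7.6.1 acknowledges hypoglycaemia with this product, and eligibility allows up to three background oral agents, sulfonylurea among them. Inconsistent dosing after a low would expose patients to avoidable risk and make the hypoglycaemia data harder to interpret.

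**Working it through.** The plan has no figure of its own to reproduce here. The check is a reading of the rules side by side, followed by arithmetic on exposure and on the cost of a skip rule.

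**Does any rule reach the morning dose?**

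- *Below-70 steps (Section 3.7).* Treatment and two rechecks take about 10 + 10 = 20 minutes, which can fit before the 10 AM dosing limit. No step mentions the capsules.
- *Below-50 rule (Section 3.7).* It counts only values up to 12 hours after a dose. If doses and tests all fall between 5 and 10 AM (an assumption), the gap from the last dose to the next fasting test runs from 19 hours (10 AM to 5 AM) to 29 hours (5 AM to 10 AM). A pre-dose fasting value therefore does not count.
- *Section 4.3.* Interruption and discontinuation rest on investigator judgement, with no glucose trigger and no instruction to the patient.
- *Section 5.3.* Daily dosing otherwise stands.
- *Section 5.7.* The bar on food before scheduled dosing refers to subjects who arrive fasting, so it appears to concern clinic visits. It is not written as a hold rule.

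**Exposure during the 12 active weeks** (run-in capsules are placebo)

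- Scheduled tests per patient: 3 × 12 = 36. The ±4-day window on Visit 8 shifts this by about 3 × 4/7 = 1.7.
- Scheduled tests in 40 patients, full enrolment and no dropout: 36 × 40 = 1,440.
- Share of readings below 70: not in the documents; assumed 0.1% to 5%.
- Share of tests done before the dose: not in the documents; assumed 50% to 100%.
- Affected patient-mornings: from 1,440 × 0.1% × 50% = 0.7 to 1,440 × 5% × 100% = 72.

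**Cost of skipping the dose after each low**

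- Once the rule fixes the order, every scheduled test precedes the dose. Average skips per patient: from 36 × 0.1% = 0.04 to 36 × 5% = 1.8.
- Planned doses: 12 × 7 = 84, or 85 if the in-clinic doses at both Visit 3 (day 0) and Visit 8 (day 84) are counted (Section 5.2.1, Table 1). 1.8/84 and 1.8/85 are both 2.1%.
- Per-protocol limit of 80% (Section 8.1.1): 0.80 × 84 = 67.2, so 68 doses are needed and 16 may be missed; 0.80 × 85 = 68, so 17 may be missed.
- Clustering at 72 lows, with no other missed doses: one patient needs 17 skips (of 84) or 18 (of 85) to fall below the limit. 72/17 = 4.2 and 72/18 = 4.0, so at most 4 of 40 patients could.
- Lowest overall rate at which even one patient could: 17/1,440 = 1.2% or 18/1,440 = 1.25%.
- Reach of the rule: 36/84 = 43% of dosing mornings (42% of 85), plus symptom-prompted readings. The other 48 or 49 mornings are unchanged.

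**The case against.** The strongest reply is that the plan already protects the patient in layers. A low must be treated, rechecked and reported. Hypoglycaemic events are adverse events (Section 7.5), so Section 4.3 lets the investigator interrupt or stop treatment. For symptoms, "Sites will instruct patients to immediately perform a finger stick glucose measurement if any symptoms occur that may be related to hypoglycemia", and patients always carry glucose tablets. Breakfast follows the dose by 30 to 45 minutes, and if glucose falls after that dose the below-50 rule applies. Values from 55 to below 70 are graded mild in Section 7.3.1. All of this stands. A reader might infer that the plan leaves patients unprotected, and the documents do not support that. What is missing is a rule for one dose on one morning.

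The gap is also conditional. It arises only in patients who test before taking the capsules, and the order is unstated.

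A reader might take the 270 and below-50 rules as proof that the below-70 branch was overlooked. They are discontinuation rules for repeated extremes, so they show only that Section 3.7 can state a consequence for study drug.

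Finally, patient-facing material (label directions, diary, consent text) is not available here. The silence is established for the protocol only, and a site instruction or diary page may already cover the point.

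None of this settles whether the capsules are taken that morning.

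**Conclusion.** The gap is real and narrow, and it should be closed. In the protocol text, a patient who tests first can meet every stated requirement and take insulin just after, or during, a fasting low.

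That the text is silent is certain; how often this matters is not. The 0.7 to 72 affected mornings span a hundredfold because both inputs are assumptions, and the documents give no size for the glucose-lowering effect of this dose. A reader might infer that such lows will be common, or that dosing after one will cause serious harm. Neither can be shown from the documents. The case rests on a foreseeable, avoidable exposure in a trial whose primary endpoint is safety, set against a very cheap remedy. It applies to the active weeks only.

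**What to change.** Add to Section 3.7, with a cross-reference in Section 5.3:

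> On test mornings, and whenever symptoms prompt a reading before the dose, do the finger-stick before the capsules. If it is below 70 mg/dL, treat as above, repeat until glucose is at or above 70 mg/dL, call the site, skip that day's capsules and record the missed dose as protocol-directed.

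Skipping is preferable to delaying. Taking the capsules after juice or glucose tablets would depart from the intended pre-breakfast regimen, and a skip needs no further decision by the patient. The medical monitor should confirm the 70 mg/dL recovery value. Section 5.3 should also say that a one-day skip under this rule is not a temporary discontinuation needing Sponsor and Medical Monitor approval to restart under Section 4.3. Section 5.5 already requires administration to be recorded, so no new form is needed.

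The cost is a few missed doses: on average about 1.8 of 84 or 85 per patient if 5% of scheduled tests are low, and fewer at lower rates. Symptom-prompted skips would add to this. Where lows cluster, a few patients could fall below the 80% per-protocol limit, so the analysis should state how protocol-directed skips count towards it. Mornings without a reading stay as they are now.

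### The timed recheck, conditional re-treatment and compulsory call for low glucose are tied to fasting values, so a single symptomatic low after breakfast has none of them in writing, however deep

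*Combined protocol and SAP*

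**What the plan says.** Section 3.7 contains three separate instructions for low glucose.

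- **Fasting value below 70 mg/dL.** "If a fasting blood glucose value is <70 mg/dL, the patient should drink 1 cup of orange juice or swallow 3-4 glucose tablets". A recheck follows: "The patient must check his blood sugar after 10 min and if the blood glucose level does not raise", the patient repeats the juice or tablets and tests again 10 minutes later. Then: "The patient must call to report this event to the study site and record all blood glucose levels in the diary".
- **Repeated deep lows after dosing.** The trigger reads: "If three or more fingerstick glucose values of <50 mg/dL (2.78 mmol/L) are observed within 12 hours subsequent to administration of study drug". It counts only when nothing such as exercise or a missed meal accounts for the readings, and study drug is then stopped. The patient is also rescued with 20 g of glucose, the episode goes in the diary, and the patient is told to contact the site.
- **Symptoms at any time.** "Sites will instruct patients to immediately perform a finger stick glucose measurement if any symptoms occur that may be related to hypoglycemia". Treatment is not to be delayed, the reading goes in the diary, and "Patients will always carry glucose tablets with them and ingest 3-4 tablets if hypoglycemia occurs".

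On timing of the dose, Section 5.2.1 says: "Patients will take 2 capsules daily in the morning 30 to 45 minutes prior to breakfast and no later than 10AM". Section 7.3.1 grades hypoglycaemia by glucose value, from mild (below 70 down to 55 mg/dL) to life-threatening (below 30 mg/dL), but attaches no patient action to any grade.

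**The concern.** The written follow-up depends on whether the patient has eaten, not on how low the glucose is. The fasting rule opens with a fasting value, and the event to be called in is that fasting event. The symptom rule sets no retest time, no call and no depth at which the response steps up.

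The primary endpoint is safety, the product is insulin, and hypoglycaemia is the only adverse event of special interest in Section 7.3. Several protections work only once the site knows about an event:

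- the investigator's decision to withdraw a patient at risk (Section 4.3);
- the 24-hour report to the sponsor for an event that qualifies as serious, which runs from notification of the site (Section 7.5.2).

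Section 5.3 plans no dose modification, so a patient who does not call may go on taking the daily dose until the next visit.

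**Working it through.** **Step 1. Compare the three rules in Section 3.7.**

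| Written step | Fasting value <70 mg/dL | Three or more values <50 mg/dL within 12 h of dosing, unexplained | Symptoms, any time |
|---|---|---|---|
| Immediate treatment | Juice or 3-4 tablets | 20 g glucose, study drug stopped | 3-4 tablets, without delay |
| Timed recheck | 10 min, and again 10 min after re-treatment | None | None |
| Re-treatment conditional on the recheck | Yes | None | None |
| Call or contact with site | Compulsory call | Contact instructed | None |
| Diary entry | Yes | Yes | Yes |

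**Step 2. Put two values through the rules**, using the grades in Section 7.3.1.

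- Fasting 69 mg/dL (mild): first column. Timed recheck and call are both required.
- One symptomatic 35 mg/dL after breakfast (severe, since 30 ≤ 35 < 40): not fasting, so the first column does not apply; one reading, so the second does not apply. Only the third remains, with no timed recheck and no call.

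**Step 3. Look for the missing instruction elsewhere.** Section 3.6 leaves unscheduled visits to the investigator. Section 4.3 lists discontinuation and stopping criteria. Sections 7.5 to 7.5.2 place recording and reporting duties on the site. None tells the patient to call for, or retest after, any low reading.

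**Step 4. How much post-dose time the fasting rule can cover.** Inputs: dose 30 to 45 minutes before breakfast (Section 5.2.1), and the 12-hour window of the repeated-lows rule (Section 3.7).

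- Before breakfast: 0.5/12 = 4.2% to 0.75/12 = 6.25%.
- After breakfast: 11.25/12 = 93.75% to 11.5/12 = 95.8%.

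A low between dose and breakfast is covered by the fasting rule and is not part of the gap.

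**Step 5. How long the site may wait.** Nominal treatment visits fall on Days 0, 7, 14, 28, 56 and 84 (Table 1).

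- Gaps: 7, 7, 14, 28 and 28 days, so the longest is 28 days (Visits 6 to 7 and 7 to 8).
- With the ±4-day windows: 28 + 4 + 4 = 36 days at most.
- Share of treatment days lying in the two long gaps: (28 + 28)/84 = 67%.
- Mean wait to the next visit, if lows were spread evenly over the 84 days: (7² + 7² + 14² + 28² + 28²)/(2 × 84) = 1862/168 = 11.1 days.

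**The case against.** The strongest reply is that such a low is neither untreated nor lost. The symptom rule applies whenever symptoms occur, so persisting symptoms can fairly be read as calling for another finger stick and more tablets. Diary lows are recorded as adverse events (Sections 3.7 and 7.5). That stands, and it narrows the gap to a missing recheck interval, a missing re-treatment step tied to the recheck, and a missing call. It does not close the gap. The protocol did not leave retesting to the patient's judgement for a mild fasting low, and confusion is among the symptoms it lists. The repeated-lows rule needs three readings, yet outside fasting no timed repeat is required.

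A second reply is that sites instruct patients, and that the diary or other patient materials may already say more. Those materials were not available, so the finding concerns the protocol text and does not show that any patient would go uninstructed.

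Third, 28 days is a maximum, and the percentages are shares of time. Both are true. The documents give no time course of drug action and no hypoglycaemia rate, so the number of affected events cannot be estimated. The 11.1-day average is the fairer typical figure, if events are spread evenly.

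Fourth, the 24-hour clock starts at site notification for every serious event, and 35 mg/dL is not serious merely because it is graded severe. Correct: the reporting delay matters only for an event that meets the Section 7.4 definition.

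**Conclusion.** The concern holds. Under Section 3.7 as written, a single symptomatic non-fasting low of any depth requires no timed recheck and no call to the site, while a mild fasting low requires both. For a dose taken as directed, with breakfast eaten 30 to 45 minutes later, 93.8% to 95.8% of the following 12 hours lies outside the fasting rule. If the patient does not report the event, the site may first hear of it at the next visit: nominally at most 28 days later, and 11.1 days on average if lows are spread evenly over treatment.

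This is a patient-safety and timeliness point about the protocol wording. Initial treatment and adverse-event capture are intact, and no planned analysis changes. It should be corrected because the remedy is cheap and the product is insulin.

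**What to change.** In Section 3.7, change the trigger of the detailed routine from a fasting value below 70 mg/dL to any glucose value below 70 mg/dL, fasting or not. In the paragraph on symptoms, refer confirmed lows to the same sequence: treat, recheck at 10 minutes, re-treat if there is no rise, and call the site. Put matching wording in the patient diary.

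No new visit, device or test is needed. The costs are a routine amendment, with ethics approval before it takes effect (Sections 10 and 11.2.3) at the 7 or 8 planned sites (2 in Israel, 3 or 4 in Belgium, 2 in the USA; Section 8.1), and extra calls to sites. These are likely to be few, but the documents give no hypoglycaemia rate from which to count them.
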